8.5.1 Follow-up report

If an SAE has not resolved at the time of the initial report and new information arises that changes the investigator's assessment of the event, a follow-up report including all relevant new or reassessed information (e.g., concomitant medication, medical history) should be submitted to the IRB. The investigator is responsible for ensuring that all SAE are followed until either resolved or stable.

8.6 Investigator Reporting of a Serious Adverse Event to Sponsor

Reporting must be consistent with regulatory, sponsor or GCRC requirements (if applicable)

8.7 Medical Emergencies

Medical emergencies that might develop during the course of the study would be referred to the patient's local emergency room.

9 STUDY ADMINISTRATION

9.1 Treatment Assignment Methods

9.1.1 Randomization

Only subjects with persistently elevated TSH (>5mIU/mL) at 6 months will be recruited for the randomization phase. After 6 months of observation, subjects will be randomized to one of two treatment arms.

- 1) 6 months of placebo followed by 6 months of levothyroxine
- 2) 12 months of levothyroxine

9.1.2 Blinding

Subjects/families will be blinded to treatment arm. Investigators will not be blinded to permit titration of levothyroxine dose.

9.1.3 Unblinding

At the conclusion of the study, subjects/families will be notified of the treatment arm they received.

9.2 Data Collection and Management

The CHOP CTIC Informatics Core will create case report forms (CRF) and a REDCap database for data capture. REDCap is an NIH-supported web-based data management software designed by Vanderbilt University investigators. Using REDCap checking tools, the BDMC will confirm completeness and valid values and will inform the investigative team of any errors or omissions for prompt resolution. Data entered in REDCap will be exported for use with Stata and SAS statistical packages as needed for immediate access to the research team.

The PIs are responsible for the accuracy and completeness of data collection and management. The PIs may designate qualified individual(s) to collect data and manage data. Only investigators and research staff that have completed appropriate IRB training and approval and are listed on the IRB approved protocol are eligible to collect and work on information from the study. Future studies that may use patients or data collected from this study must have separate approved IRB protocols and consent forms, if applicable.

Recruitment data will be recorded onto the screening questionnaire after the verbal consent is recorded. Original data will be recorded directly onto CRFs by the study coordinator or a study investigator. Copies of laboratory, physical exam, anthropometric, DXA, PWV, and PWA results will be received through inter-office mailing, picked up directly, and sometimes through email. This information also will be recorded onto CRFs while the originals may be kept at the testing site (CHOP Outpatient CTIC) or with the study investigative staff. CRFs will be kept in a locked filing cabinet in a locked room at all times.

All information will be transferred to a REDCap password-protected database, located on a secure sever supported by the CHOP Research Institute. The password to log onto the database will be unique to each member of the study team. CNMC study staff will be assigned to a REDcap user group that will restrict their access so they may edit solely the information of subjects enrolled at CNMC. The CNMC Principle Investigator will have access to view/edit data of all subjects. Note that only limited PHI (date of visit, date of birth) is included in the REDcap database. CHOP will have read-write access for data collected at both sites. CHOP will require access to edit records for both sites because several evaluations will be analyzed at CHOP, and reports including data from both CHOP and CNMC sites will be forwarded to the CHOP team, who will then import or enter the data into REDCap. Written informed consent granting permission for other site(s) to access PHI will be obtained from all subjects. The CRF and REDcap database will be designed by the CTRC Informatics Services.

All data and records generated during this study will be kept confidential in accordance with institutional policies and on HIPPA subject privacy. The investigators/study team members/site personnel will not use such data and records for any purpose other than for conducting the study.

As a way to minimize the chance of PHI (protected health information) from being disclosed, a unique identification code will be used for each participant. The key to this code will be kept in a locked file in the PI/Study Coordinator's office.

If any publications result from this research, the participant will not be identified by name/PHI.

The information collected as part of this study will be kept for 6 years or until the completion of the study (whichever is longer). At that time, the information collected will be destroyed or all identifiable information will be removed. All keys will be destroyed at this time, as well.

9.3 Confidentiality

All data and records generated during this study will be kept confidential in accordance with Institutional policies and HIPAA on subject privacy and the Investigator and other site personnel will not use such data and records for any purpose other than conducting the study.

No identifiable data will be used for future study without first obtaining IRB approval. The investigator will obtain a data use agreement between the provider (the PI) of the data and any recipient researchers before sharing a limited dataset (PHI limited to dates and zip codes).

9.4 Regulatory and Ethical Considerations

9.4.1 Data and Safety Monitoring Plan

Study progress and safety will be reviewed quarterly (and more frequently if needed) by the PI. Review of the rate of subject accrual, adherence to inclusion/exclusion criteria will occur quarterly to assure that participants meet the eligibility criteria. There will be ongoing collection of data on adverse events and compliance to the treatment protocol throughout the study by research staff, which will be reviewed monthly by the study team and PI. If there is an incidental finding deemed by the PI to be clinically relevant, the primary care provider will be notified. The parent/guardian will be notified and asked to follow up with the subject's primary care provider if during the visit a subject is noted to have blood pressure that is \geq the 95th percentile for age, gender, and height. We will notify the parent/guardian/primary care provider with clinically relevant abnormal labs. Specifically, these include: lipid levels/insulin levels/blood glucose levels /TSH and T4. Note that some labs, such as lipids and insulin, are run in batches and reporting of results may be delayed.

Data Monitoring Board (DSMB) -- Interim monitoring and analysis

A data safety monitoring board (DSMB) will be established: (1) to protect study patients, (2) to safeguard their interests, (3) to monitor the overall conduct of the trial, (4) to help to protect the integrity of the trial, and (5) to supervise the conduct of any interim analyses. Specific rules and protocols for all reviews will be established in a formal protocol, and approved by the DSMB, prior to the first DSMB meeting. The DSMB will work jointly with the trial statisticians and clinical investigators to establish specific criteria to accomplish its tasks. The DSMB will consist of at least four members including a biostatistician, a developmental pediatrician from outside Children's Hospital of Philadelphia, a pediatric endocrinologist, and a senior faculty member with experience in clinical research and in care of children and adolescents with complex chronic illness. The DSMB will choose its chair.

The Project PI will establish procedures for identifying classes of AEs, documenting them on an Adverse Experience Report (AER) form, and then reporting them regularly to the DSMB(33) .

The DSMB will meet annually to review efficacy issues and adverse events, and will have additional conference calls as needed. Annual reports will be prepared for them by the CHOP Data Management Core. The DSMB will independently evaluate whether adverse events constitute grounds to discontinue the study.

The DSMB will report to the trial principal investigators within one month of the start of the DSMB meeting, or earlier if patient safety becomes an issue. Early stopping determinations will be limited to considerations of safety and adverse events; owing to the small sample size, there will be no formal early stopping rule for superiority or futility.

DSMB reporting; Independence of DSMB and study trial leadership

All data and the interim analyses will be conducted by the DSMB and the project statisticians, independently from the trial leadership and staff. The DSMB report will consist of the following elements:

DSMB monitoring plan and summary of report
Major protocol changes
Study accrual by month
Any violations of eligibility
Demographics
Adherence to medication
Dropout and loss to follow up
Analysis of endpoints for safety
Report of any adverse events
Formal recommendation on early stopping
Recommendations for notification to IRB

It will be the responsibility of the trial leadership to notify the IRB or IRBs involved of any issues that are relative to patient safety or to early stopping of the study.

9.4.2 Risk Assessment

The risks of participating in this study are relatively small and the investigators believe the overall study is of minimal risk to the participants.

Expected risks to the subject are as follows:

- Blood draw may result in temporary discomfort from the needle stick, bruising, fainting, weakness, and rarely an infection at the site
- Anthropometric measurements and pubertal status exam pose minimal risks
- Exposure to radiation during DXA scan
- Sharing of private health information (PHI) including dietary intake, demographic information, health history and medical information
- Pulse wave velocity and pulse wave analysis pose minimal risks
- 12 hour overnight fasting may cause hunger pangs, upset stomach, headache, or light-headedness
- Blood pressure measurement by auscultation may cause temporary numbness/tingling in the arm
- SenseWear® Armbands worn for 7 consecutive days may cause skin irritability
- Sensitive psychosocial issues may arise during questionnaire assessment

A small amount of blood (about 3 teaspoons) will be drawn at major assessment points. Adolescents may experience some degree of discomfort, bruising, or lightheadedness with fasting blood draws. There is also a risk of infection when blood is drawn. These occurrences are rare, generally mild, and respond to conservative treatment.

Participation in the study involves risks associated with the small amount of radiation exposure associated with the DXA whole body scan for body composition assessment; the total radiation EDE from DXA scans is less than 3 μ Sv (or 1 mrem). This total amount of radiation is less than the exposure to daily background radiation at sea level (3,000 μ Sv per year) and is therefore considered minimal risk. Females of childbearing potential undergo a urine pregnancy test prior to the DXA scans. Pregnant females do not have DXA scans performed in order to protect the unborn fetus.

The anthropometric assessment involves measurements of height, weight, circumferences and skinfold thickness. There is a very minor possibility of bruising from the skinfold thickness measurements. The exam will be performed by trained anthropometrists experienced in obtaining measurements in children at all levels of cognitive ability. The measurements are obtained in a private room. The parent is permitted to stay with the child if it increases their comfort with the exam.

The puberty assessment will be performed by a pediatric endocrinologist in a private setting. The procedure will be explained to the child in advance, and the parent is permitted to be present if preferred by the child. The exam is performed by highly experienced personnel who are familiar with minimizing distress associated with the exam.

SenseWear® Armbands (Body Media, Inc.). There is little to no risk associated with measuring physical activity, sedentary behavior, and sleep with armband accelerometers. These accelerometers fit comfortably on the participant's arm and can easily be removed should he/she become uncomfortable. Some patients may experience skin irritation, particularly when sweating, with the devices in which case they can adjust them or in rare instances, remove them if necessary. To prevent irritation, parents will be instructed to clean the armband with mild soap and water when the child removes it to bathe or shower. If irritation does occur, parents will be instructed to use Aquaphor or Vaseline where the fabric of the band is to treat and prevent further irritation. If a child is allergic to metal they will not be required to complete this assessment.

A licensed clinical psychologist with expertise in working with children and adolescents, will meet with families concerning sensitive psychosocial issues that may arise during assessments or intervention. Any emotional upset will be handled with appropriate support to the participants and their caregivers. Further, if a behavioral health concern arises during the study needing further evaluation and treatment, the clinical psychologist will assist with a referral.

If a subject shows any signs of clinical instability or definitively decides to discontinue participation, the study visit will end.

Protection against risks associated with thyroid hormone treatment

Children and adolescents with subclinical hypothyroidism are commonly treated with thyroid hormone replacement, even in the absence of data supporting treatment. Similarly, subclinical hypothyroidism is frequently treated in the setting of DS despite a dearth of evidence to support or negate intervention. The primary risk of thyroid hormone treatment in this 6 month observation followed by 6-12 month intervention study is excessive replacement leading to relative hyperthyroidism with TSH suppression; short-term symptoms include restlessness, irritability, tachycardia, palpitations, poor sleep, and weight loss. To minimize these risks:

- The family will be instructed to observe and report these symptoms/signs to the study team
 - TSH and T4 will be checked if signs/symptoms develop
-

-
- TSH and T4 will be checked 6 weeks after levothyroxine initiation, the time required to reach steady state; the dose will be titrated to maintain TSH in the normal range
 - If the initial TSH is within range, TFTs will be checked in another 14 weeks, sooner if symptoms arise
 - If a TSH is elevated or suppressed, the dose will be adjusted and TFTs repeated in 6 weeks to reassess thyroid status

The dose of levothyroxine replacement (0.5-1 mcg/kg/dy) is not expected to cause TSH suppression and symptoms of hyperthyroidism. A dose of 1 mcg/kg/day is used in the treatment of subclinical hypothyroidism in adults and is much lower than typical full replacement doses of 4-5 mcg/kg/day for age 6-12y; 2-3 mcg/kg/day for age >12 y but growth and puberty incomplete; and 1.7 mcg/kg/day for children in whom growth and puberty are complete. In fact, chronic suppressive doses of levothyroxine are routinely used following thyroidectomy and radioactive iodine ablation for thyroid cancer in adults and children. For children, this treatment means TSH is maintained in the low range (TSH < 0.1 mIU/L).(34); the major concern is the impact of years of suppressive therapy upon bone health. In this study, TSH will be measured and dose adjustments made for low TSH; thus, any subclinical hyperthyroidism induced by levothyroxine therapy will be brief. Morbidity from acute levothyroxine intoxication requires massive doses of levothyroxine (> 5-10 mg) and is not anticipated. The study team will remind families that, as with all medications, administration should be supervised by a parent and medications maintained out of reach of children.

The study team will review potential side effects and toxicities with subjects by telephone 4 weeks after treatment initiation. If symptoms are present, TSH and T4 will be checked and dose adjustments made if necessary. If symptoms are absent, TSH and T4 will be checked as scheduled and symptoms reviewed at 6 weeks. All symptoms will be recorded. The Investigative team will have immediate access to TSH and T4 when these data are available from the lab. Thyroid function data will also be reviewed monthly by the study team, to assess study dosing practice.

For subjects enrolled in this study, any subject who develops TSH > 10 mIU/L during the course of the study will have a repeat TSH test done within 1-2 weeks. If the repeat TSH remains > 10 mIU/mL, the subject will be withdrawn from the study and referred to endocrinology for management of hypothyroidism. If a suppressed TSH (TSH < 0.1 mIU/L) is identified in a child on placebo, the TSH will be repeated within 2-3 weeks. If the TSH remains suppressed the subject will be referred to endocrinology for management of possible hyperthyroidism. If a suppressed TSH (TSH < 0.1 mIU/L) is identified in a child on levothyroxine, the levothyroxine dose will be decreased and the lab repeated within 4-6 weeks. If the TSH remains suppressed or child has symptoms consistent with hyperthyroidism, the TSH will be discontinued and the TSH repeated in 6 weeks. If the TSH remains suppressed the subject will be referred to endocrinology for management of possible hyperthyroidism,

At the completion of the study, serum TSH and T4 will be measured, thyroid hormone replacement will be discontinued, and thyroid hormone results from the study reported to the PMD. The subject will be directed to follow-up with the primary care provider or with pediatric endocrinology to determine if continued thyroid hormone replacement is appropriate.

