3.1.3 Treatment Phase

Randomization and blinding -

Only subjects with persistently elevated TSH (5 – 10 mIU/mL) will be randomized into the following 2 groups of 10: Group 1 (Delayed treatment) or Group 2 (Immediate treatment). A 3 month supply of placebo will be dispensed to subjects that have been randomized into Group 1 and a 3-month supply of levothyroxine will be dispensed to subjects randomized into Group 2.

Blood Draw Visit B (7.5 Month): TSH and T4 will be measured 6 weeks after the Study Visit #2 (approximately 7.5 months from the start of the study). Subjects will obtain a blood draw. Dose adjustments will be made for Group 2 as needed. Another 3-month supply of placebo or levothyroxine (dose adjusted as necessary) will be mailed to the home. Subjects requiring dose adjustments will have TSH and T4 in another 6 weeks to confirm/assure TSH is in the desired range.

Study Visit #3 (12 Month): – Subjects and their parents/guardians will present to the research facility following a 12-hour overnight fast. At this study visit, the subject will have the following measures: fasting blood samples, TSH, T4, anthropometric measurements, whole body DXA scan, blood pressure, pubertal assessment and questionnaire assessments. Females will receive a urine pregnancy test. Females found to be pregnant will be disqualified from the study and will receive appropriate counseling and referral. After the study visit, subjects will be asked to wear a physical activity arm band at home for 7 days, and a 3 day dietary recall will be done by telephone. TSH and T4 will be reviewed and levothyroxine will now be dispensed to both Groups 1 and 2. Group 2 will continue on current dose if TSH within range; otherwise dose adjustments will be made as necessary.

Blood Draw Visit C (13.5 Month): TSH and T4 will be measured 6 weeks after the 12 month visit (approximately 13.5 months from the start of the study). Subjects will have blood drawn. A subsequent blood draw 6 weeks later will be required for any dose adjustments.

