4.4 Blood Draw Visits B & C

Randomized subjects will be asked to have a blood draw to check TSH and T4 levels 6 weeks after the 6 month and 12 month visits. TSH will be repeated 6 weeks after any dose adjustment. The purpose to for this check is to adjust the levothyroxine dose if the PI deems necessary.

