Key contrasts will compare the level of each endpoint before and after treatment by comparing differences of model-based expected values at the end of treatment and expected values at baseline; expected values arise from implementation of mixed effects models. This approach permits adjustment for relevant changes in patient characteristics over time (e.g. changes in growth and pubertal status) and for any baseline factors predicting dropout. Alternative contrasts will compare slopes of endpoints over time prior to the intervention against the slopes after treatment initiation. Pre-intervention measures will improve statistical power.

Sensitivity analyses will examine the potential impact of informative dropout⁽³¹⁾, although this source of bias will be minimized through subject retention and follow-up after dropout⁽³²⁾. Supplementing models will be complete descriptive reports, including graphical displays of cholesterol and BMI-Z trajectories for each subject.

Potential Problems/Feasibility: Dosing of levothyroxine treatment tends to be weight-based and is not an exact science. The starting daily dose of 0.5-1 mcg/kg/day is less than

full replacement doses since TSH will be in the 5-10 mUI/mL range and we wish to avoid “over-supplementing” and suppressing TSH. TSH will be rechecked 6 weeks after levothyroxine initiation to confirm TSH is in the desired range. After 6 weeks some subjects may not have “optimal” TSH levels and dose adjustments will be required. We expect that by 3 months following levothyroxine initiation, all subjects will have TSH in the desired range, allowing an additional 3 months for the effect of intervention to be realized; in fact, the immediate treatment group will be followed for 12 months, over which time effects upon body composition and CMR factors should be apparent. This study might find that the relationship between subclinical hypothyroidism and CMR factors is pure association, an important finding as the medical community looks for evidence upon which to base management of “mild” TSH elevations in DS. In fact, this finding could avert unnecessary treatment of subclinical hypothyroidism in adolescents with DS.

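### Section 9.4.2 withdraws a child on levothyroxine whose TSH is confirmed above 10 at 1-2 weeks, with no titration step and no stated outcome follow-up (minor)

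*Combined protocol and SAP*

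**What the plan says.** Two rules in section 9.4.2 reach a child who is taking levothyroxine and has a TSH above 10.

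- The bullets on limiting the risks of treatment say: "If a TSH is elevated or suppressed, the dose will be adjusted and TFTs repeated in 6 weeks to reassess thyroid status". They set no upper limit on what counts as elevated. They also give the reason for the 6-week interval: "TSH and T4 will be checked 6 weeks after levothyroxine initiation, the time required to reach steady state".
- Later in the section, the rule for high values says that "any subject who develops TSH > 10 mIU/L during the course of the study will have a repeat TSH test done within 1-2 weeks". It continues: "If the repeat TSH remains > 10 mIU/mL, the subject will be withdrawn from the study and referred to endocrinology". It does not mention a dose change and does not distinguish children on drug from children on placebo.

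Other sections set out the titration plan. Section 4.4 says of the 6-week blood draws: "The purpose to for this check is to adjust the levothyroxine dose if the PI deems necessary". Section 3.1.3 adds: "Subjects requiring dose adjustments will have TSH and T4 in another 6 weeks to confirm/assure TSH is in the desired range". Section 6.1.1 explains that the starting dose is deliberately below full replacement and that some children will need adjustment, and states: "We expect that by 3 months following levothyroxine initiation, all subjects will have TSH in the desired range".

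On missing data, section 6.1.1 plans dropout-weighted estimating equations and sensitivity analyses for informative dropout. It counts on retention and continued follow-up of children who drop out to limit that bias.

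**The concern.** Repeating the test and then referring suits an untreated child. In the observation phase a confirmed value above 10 means that the condition is no longer subclinical (sections 3.1 and 9.4.3). In a child on a low starting dose, the same value may mean only that the dose is too small or the tablets are not being taken. The rest of the plan answers that by titrating.

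Two things are at stake. First, a randomised child can be lost before the adjustment that the treatment strategy depends on. Second, the child leaves the study, not just the study drug, because of a value measured after randomisation that levothyroxine is meant to change. Section 9.4.2 does not say that any outcome visit is kept, so outcomes could be missing for a reason related to both arm and response.

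**Working it through.** No figure in the plan bears on this, so the check sets the rules side by side and then works out the timing.

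**Rules compared**

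| Situation | Action | Section |
|---|---|---|
| TSH above 10, observation phase | Repeat in 1-2 weeks; if confirmed, not randomised, referred | 3.1, 3.1.2, 6.3, 9.4.3 |
| TSH raised, on levothyroxine | Adjust dose, retest in 6 weeks | 9.4.2 (bullets), 3.1.3 |
| TSH above 10, any subject, any time | Repeat in 1-2 weeks; if confirmed, withdrawn and referred | 9.4.2 (later text) |
| TSH below 0.1, on placebo | Repeat in 2-3 weeks, then refer | 9.4.2 |
| TSH below 0.1, on levothyroxine | Lower dose, retest in 4-6 weeks, further steps before referral | 9.4.2 |

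A treated child with a TSH of 11 falls under both the second and third rows. I looked for a statement of precedence in every section that deals with TSH above 10 or dose adjustment, including the payment section (9.7), and found none. The last two rows show that the section has a drug-specific branch for low TSH. It has no matching branch for high TSH.

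**Timing, Group 2 child above 10 at month 7.5**

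Inputs: first check 6 weeks after starting drug; repeat 1-2 weeks later; retest 6 weeks after a dose change; month-12 visit 6 months after starting, taken as 26 weeks; 3 months taken as 13 weeks. I assume that drug starts at month 6 and that the dose is changed at the first check.

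- Withdrawal decision: 6 + 1 to 6 + 2 = weeks 7-8.
- Time from there to month 12: 26 - 8 to 26 - 7 = 18-19 weeks.
- Gap to the 3 months that section 6.1.1 allows for reaching range: 13 - 8 to 13 - 7 = 5-6 weeks.
- Retest under the dose-adjustment bullet: 6 + 6 = week 12, inside those 13 weeks and 26 - 12 = 14 weeks before month 12.

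**If the two rules are run together**

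If the dose is raised first and withdrawal is then decided on the 1-2 week repeat, that value comes 6 - 2 to 6 - 1 = 4-5 weeks short of the section's own steady-state interval. This shortfall applies only when the dose is raised before the repeat. If the dose is left alone, the repeat is simply a confirmatory test.

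**Scale**

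One child is 1/10 = 10% of a planned group of 10. The recruitment allowance is 29 - 20 = 9 children, but it must also cover children not randomised after observation.

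**The case against.** The strongest defence is that the rule for values above 10 is the specific one. It names a threshold, covers every subject throughout the study, and so displaces the general dose-adjustment bullet, which sits in a list aimed mainly at over-replacement. The authors separated placebo from levothyroxine for low TSH, so leaving high TSH unseparated may be deliberate. The trial concerns TSH of 5-10, and referring a child confirmed above 10 is a cautious safety choice. The rule also treats both arms alike.

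Part of this stands. The specific-over-general reading is reasonable, and a reader who infers that the two rules flatly contradict each other goes too far, because a team could follow both. But if the high-TSH rule governs, it removes a child on a deliberately low dose with no titration step, against sections 3.1.3, 4.4 and 6.1.1. Discretion does not help: dose changes are left to the PI, but withdrawal is mandatory.

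The objection is also right that the event should be rare. Children are randomised with TSH of 5-10, section 6.1.1 expects control within 3 months, and section 7.1.4 provides weekly adherence contact. Section 4.6 already allows discontinuation for non-adherence, so that route to loss is not new.

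A reader might infer that the two sites would apply the rules differently. The documents do not support this: dosing rests with the PI, and section 9.4.2 provides monthly team review of thyroid results to assess dosing practice.

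**Conclusion.** The point holds as a minor one. For children on levothyroxine, the mandatory withdrawal rule in section 9.4.2 conflicts with the dose-adjustment bullet in the same section and with the titration plan elsewhere. It also sits poorly with the reliance on follow-up after dropout in section 6.1.1.

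The documents do not support a claim of material bias or lost power. They give no rate of TSH above 10 on drug or on placebo, the recruitment allowance may absorb a few removals, and the planned weighting and sensitivity analyses would soften the effect. Nor is it certain that outcome collection would stop. Section 9.4.2 is silent, and section 6.1.1 implies that some follow-up continues, so the most that can be said is that it may stop. The 18-19 week figure assumes a Group 2 child first found above 10 at month 7.5 and withdrawn at the repeat.

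**What to change.** Amend the high-TSH rule in section 9.4.2, with clinical confirmation of item 1.

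1. Add a branch for children on levothyroxine. For TSH above 10, check adherence, raise the dose, retest 6 weeks later, and refer if the value is still above 10. Keep the 1-2 week repeat and referral for untreated children (observation phase or placebo).
2. For a randomised child in either arm who is referred for confirmed TSH above 10, state that study treatment stops but the scheduled month-12 and month-18 outcome visits are kept, in place of withdrawal from the study.

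The cost is protocol wording and usually one draw outside the schedule. No extra draw is needed after a dose change at month 12, because the 6-week retest is then the month-13.5 draw. Section 9.7 already pays for up to 3 additional checks.

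There are three downsides. A treated child above 10 waits 6 - 2 to 6 - 1 = 4-5 weeks longer before referral. In months 6-12, study treatment would stop sooner on placebo than on levothyroxine, so the change protects outcome collection but does not equalise time on assigned treatment. A placebo child who starts levothyroxine outside the study and keeps the month-12 visit would somewhat dilute the comparison at that visit.
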